6.8.3.10 Arterial thromboembolism

Arterial thromboembolic events (including transient ischemic attack and ischemic stroke) have been reported in clinical studies with cediranib. Cediranib should be used with caution

in patients who are at an increased risk of thrombotic events or who have a history of thrombotic events. Cediranib should be permanently discontinued in patients who develop an arterial thromboembolic event.

6.8.3.11 Venous thromboembolism

Venous thromboembolic events including pulmonary embolism and deep vein thrombosis have been commonly reported in patients treated with cediranib. Anticoagulant treatment should be started in accordance with clinical practice. Discontinuation of cediranib may be considered. Cediranib should be used with caution in patients at risk of venous thromboembolism.

6.8.3.12 Wound healing

Treatment with cediranib should be stopped at least 2 weeks prior to scheduled surgery. The decision to resume cediranib therapy after surgery should be based on clinical judgment of adequate wound healing. In patients who experience wound healing complications during therapy, treatment with cediranib should be interrupted until the wound is fully healed. No formal studies of the effect of cediranib on wound healing have been conducted; however, in the ICON6 pivotal study there was no evidence of an increase in wound healing complications in cediranib treated patients compared with placebo.

6.8.3.13 Elderly

There is a limited amount of safety data available for cediranib use in patients aged 75 years and older. Based on a population PK analysis, the clearance of cediranib decreased with age, however, no dose adjustment is needed given the small impact on exposure or variability. Caution should be taken when treating patients who are aged 75 years or older with cediranib. In case of toxicity dose pause or dose reduction may be considered.

6.8.3.14 Mild/moderate renally impaired patients

Patients with mild and moderate renal impairment discontinued cediranib more often due to adverse events, particularly when cediranib was co-administered with chemotherapy. Population PK analysis showed that no adjustment of cediranib dose is required in this population as cediranib is minimally renally cleared; however, cediranib clearance may be decreased in patients with low body weight. In the ICON6 pivotal study, patients with mild or moderate impairment had lower median body weight compared with patients with normal renal function. Caution should be exercised in patients with mild and moderate renal impairment and a cediranib dose adjustment should be considered in case of signs of toxicity.

For information on use of olaparib in renally-impaired patients, please see Section [6.8.4.4](#)

6.8.3.15 Weight decreased

In the ICON6 study, weight decreased was very commonly reported in cediranib treated patients. Weight loss ($\geq 7\%$) in cediranib-treated patients was associated with higher incidence of decreased appetite, vomiting and stomatitis, although these events were also commonly reported in patients who did not lose weight.

6.8.4 Management of olaparib associated toxicity

6.8.4.1 Management of MDS/AML

Patients who develop MDS/AML on treatment should be discontinued from olaparib treatment and managed appropriately.

6.8.4.2 Management of olaparib-related new or worsening pulmonary symptoms

If new or worsening pulmonary symptoms (eg, dyspnea) or radiological abnormalities occur in the absence of a clear diagnosis, an interruption in 1 or both IPs dosing is recommended and further diagnostic workup (including a HRCT scan) should be performed to exclude pneumonitis.

Following investigation, if no evidence of abnormality is observed on CT imaging and symptoms resolve, then IP(s) can be restarted, if deemed appropriate by the investigator. If significant pulmonary abnormalities are identified, these need to be discussed with the Study Physician.

6.8.4.3 Management of nausea and vomiting

Events of nausea and vomiting are known to be associated with olaparib treatment. In study D0810C00019 nausea was reported in 71% of the olaparib treated patients and 36% in the placebo treated patients and vomiting was reported in 34% of the olaparib treated patients and 14% in the placebo treated patients. These events are generally mild to moderate (CTCAE Grade 1 or 2) severity, intermittent and manageable on continued treatment. The first onset generally occurs in the first month of treatment for nausea and within the first 6 months of treatment for vomiting. For nausea, the incidence generally plateaus at around 9 months, and for vomiting at around 6 to 7 months.

No routine prophylactic anti-emetic treatment is required at the start of treatment with the IPs, however, patients should receive appropriate anti-emetic treatment at the first onset of nausea or vomiting and as required thereafter, in accordance with local treatment practice guidelines. Taking olaparib tablets with food may help alleviate symptoms of nausea and vomiting.

As per international guidance on anti-emetic use in cancer patients (European Society for Medical Oncology [ESMO], NCCN), generally a single agent antiemetic should be considered eg, dopamine receptor antagonist, antihistamines or dexamethasone.

6.8.4.4 Management of renal impairment

If subsequent to study entry and while still on study treatments, a patient's estimated creatinine clearance (CrCL) falls below the threshold for study inclusion (<50 mL/min), retesting should be performed promptly. A dose reduction of olaparib is recommended for patients who develop moderate renal impairment (calculated CrCL by Cockcroft-Gault equation of ≥ 31 mL/min and ≤ 50 mL/min) for any reason during the course of the study: the dose of olaparib should be reduced to 150 mg bd.

Because the CrCL determination is only an estimate of renal function, in instances where the CrCL falls to between 31 mL/minutes and 50 mL/minutes, the Investigator should use his or her discretion in determining whether a dose change or discontinuation of therapy is warranted.

Olaparib has not been studied in patients with severe renal impairment (CrCL \leq 30 mL/minutes) or end-stage renal disease; if patients develop severe impairment or end stage disease it is recommended that olaparib be discontinued. For information on use of cediranib in renally-impaired patients, please see Section 6.8.3.14.

6.8.5 Interruptions for intercurrent non-toxicity related events

IP(s) dose interruption for conditions other than toxicity resolution should be kept as short as possible. If a patient cannot restart IP(s) within 3 weeks for resolution of intercurrent conditions not related to disease progression or toxicity, the case should be discussed with AstraZeneca study physician.

All dose reductions and interruptions (including any missed doses), and the reasons for the reductions/interruptions are to be recorded in the eCRF.

Both IPs should be stopped at least 2 weeks prior to planned surgery. After surgery both IPs can be restarted when the wound has healed. No stoppage of IPs is required for any needle biopsy procedure.

Both IPs should be discontinued for a minimum of 3 days before a patient undergoes radiation treatment. Both IPs should be restarted within 3 weeks as long as any bone marrow toxicity has recovered.

Because the AEs related to olaparib may include asthenia, fatigue and dizziness, patients should be advised to use caution while driving or using machinery if these symptoms occur.

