6.8 Management of IP related toxicities

The dose levels and the general approach to dose modification of the cediranib and olaparib component of the combination therapy are shown in Table 7 and Table 8, respectively. Specific dose modification information for some AEs are provided in Section 6.8.3 and Section 6.8.4. Please refer to the current IBs for emerging safety data for cediranib and olaparib: CCI

AEs should be treated with the appropriate maximum supportive care, and dose reductions should be clearly documented in the eCRF.

Table 7 Dose modification cediranib

Dose Level	Cediranib tablets
Initial dose	30 mg daily
Dose reduction 1	20 mg daily
Dose reduction 2	15 mg daily

Table 8 Dose modification of olaparib

Dose Level	Olaparib tablets
Initial dose	200 mg twice daily
Dose reduction 1	150 mg twice daily
Dose reduction 2	100 mg twice daily

At the discretion of the investigator, the study drugs may be held or dose modified independently if the observed toxicity is attributed to only one of the drugs, while the patient continues to receive the drug not associated with the observed toxicity. The time a given drug is held should not exceed 3 weeks. Once dose of study drug(s) have been reduced, no dose re-escalation is permitted.

If treatment has to discontinue due to toxicity, both IPs (cediranib and olaparib) should be discontinued at the same time; patients are not allowed to remain in the study if they are taking either cediranib or olaparib as monotherapy. However, in rare circumstances, patients experiencing ongoing clinical benefit but who develop one of the toxicities listed below related to one of the IPs that prevents them to continue to take this IP, may be allowed to continue on the unrelated drug if in the opinion of the treating investigator the risk benefit remains favorable and only after discussion with the AstraZeneca Study Physician and the Principal Investigator.

AEs requiring cediranib to be discontinued:

- GI perforation
- Arterial Thromboembolic Event
- PRES
- Severe hemorrhage
- Severe persistent hypertension despite maximal anti-hypertensive treatment

AEs requiring olaparib to be discontinued:

- Bone marrow findings consistent with MDS/ AML
- Severe persistent anemia
- Pneumonitis

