7.7 Concomitant and other treatments

The Investigator must be informed as soon as possible about any medication taken from the time of screening until the end of the study treatment period (treatment discontinuation or FPV visit). Any concomitant medication(s), including herbal preparations, taken during the study will be recorded in the eCRF.

Medications that should NOT be administered

No other anti-cancer therapy (chemotherapy, immunotherapy, hormonal therapy (Hormone replacement therapy (HRT) is acceptable), RT, biological therapy or other novel agent) is to be permitted while the patient is receiving one or both IPs.

Live virus and bacterial vaccines should not be administered whilst the patient is receiving one or both IPs and during the 30 day follow up period. An increased risk of infection by the administration of live virus and bacterial vaccines has been observed with conventional chemotherapy drugs and the effects with the combination of cediranib and olaparib are unknown.

The use of any natural/herbal products or other “folk remedies” should be discouraged; but use of these products, as well as use of all vitamins, nutritional supplements and all other concomitant medications must be recorded.

Cediranib and inducers of PgP/UGT

In vitro data indicate that cediranib is unlikely to cause interactions with CYP450 inducers, inhibitors, and substrates. Cediranib oxidative metabolism appears to be mediated by flavin-containing monooxygenase enzymes FMO1 and FMO3 and glucuronidation by UGT1A4. Co-administration of cediranib with strong inducers of PgP/UGT decrease cediranib plasma concentrations; therefore, use of potent inducers of UGT/PgP (eg, rifampicin, carbamazepine, phenobarbital, phenytoin and St. John Wort) should be avoided if possible. Cediranib is a substrate of MDR1 (Pgp), and possible substrate of breast cancer resistant protein (BCRP). Cediranib is not an inhibitor of OAT1 and OAT3, but it has a low potential to inhibit MDR1 (Pgp), BCRP, OATP1B1, OATP1B3, OCT2, MATE1. The clinical impact of this finding is unknown. Cediranib may act as an inhibitor of renal tubular MATE2-K, this could increase exposure of co-administered agents such metformin or to endogenous agents such as creatinine; however, the ICON6 study showed that increases of blood creatinine caused by 20 mg/day cediranib treatment were infrequent (4.4%) and only mild in severity, suggesting the clinical impact of renal tubular MATE2-K inhibition by cediranib is small.

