Patients who are taking warfarin may participate in this trial; however, it is recommended that prothrombin time (International Normalized Ratio [INR] and activated partial thromboplastin time) be monitored carefully at least once per week for the first month, then monthly if the INR is stable. Subcutaneous heparin and low molecular weight heparin are permitted.

Anti-emetics/Anti-diarrheal

From screening onwards, should a patient develop nausea, vomiting and / or diarrhea, then these symptoms should be reported as AEs (see Section 6.3) and appropriate treatment of the event given.

Palliative radiotherapy

Palliative RT may be used for the treatment of pain at the site of bony metastases that were present at baseline, provided the investigator does not feel that these are indicative of clinical disease progression during the study period. Both IPs should be discontinued for a minimum of 3 days before a patient undergoes therapeutic palliative radiation treatment. Both IPs should be restarted within 4 weeks as long as any bone marrow toxicity has recovered.

Administration of other anti-cancer agents

Patients must not receive any other concurrent anti-cancer therapy, including investigational agents, while on one or both IPs. Patients may continue the use of bisphosphonates or denosumab for bone disease and corticosteroids for the symptomatic control of brain metastases provided the dose is stable before and during the study and they were started at least 4 weeks prior to the first doses of IPs.

Subsequent therapies for cancer

Details of first and subsequent therapies for cancer and/or details of surgery for the treatment of the cancer, after discontinuation of treatment, will be collected until the end of the study.

Other concomitant treatment

Other medication other than that described above, which is considered necessary for the patient's safety and well-being, may be given at the discretion of the Investigator and recorded in the appropriate sections of the eCRF.

In addition, any unplanned diagnostic, therapeutic or surgical procedure performed during the study period must be recorded in the eCRF.

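### Protocol 6.8.5 and 7.7 give different limits, 3 and 4 weeks, for restarting both study drugs after radiotherapy, and neither says when the window starts

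*Protocol*

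**What the plan says.** Two sections of the current protocol cover stopping and restarting the study drugs around radiotherapy.

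- **Section 6.8.5** (interruptions not due to toxicity): "Both IPs should be discontinued for a minimum of 3 days before a patient undergoes radiation treatment". The next sentence reads: "Both IPs should be restarted within 3 weeks as long as any bone marrow toxicity has recovered".
- **Section 7.7** (paragraph on palliative radiotherapy): "Both IPs should be discontinued for a minimum of 3 days before a patient undergoes therapeutic palliative radiation treatment". The next sentence reads: "Both IPs should be restarted within 4 weeks as long as any bone marrow toxicity has recovered".

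Section 7.7 also settles which radiotherapy is allowed. Its list of barred therapies ends "RT, biological therapy or other novel agent) is to be permitted while the patient is receiving one or both IPs". The exception follows later in the section: "Palliative RT may be used for the treatment of pain at the site of bony metastases that were present at baseline". It applies only where the investigator does not regard the pain as a sign of clinical progression.

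Section 6.8.5 opens with a general rule for interruptions of this kind. Its condition is "If a patient cannot restart IP(s) within 3 weeks for resolution of intercurrent conditions not related to disease progression or toxicity". What follows from it is a discussion with the sponsor's study physician.

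**The concern.** Sites are given two different limits for the same action. Restart involves two drugs and is conditional on marrow recovery, and the protocol plans for approximately 40 sites. A site working from 7.7 could let a patient run into a fourth week without knowing that 6.8.5 sets a shorter limit and, for intercurrent conditions, a discussion point at 3 weeks. A site working from 6.8.5 would treat the same patient as overdue. What is at stake is uniform handling of these patients, and a single standard for anyone later judging whether a restart followed the protocol.

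**Working it through.** The plan states no figure that can be reproduced, and no sample size, power or event count is involved. The check sets the passages side by side.

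| Item | Section 6.8.5 | Section 7.7 |
|---|---|---|
| Event named | radiation treatment | therapeutic palliative radiation treatment |
| Drugs stopped before it | both, at least 3 days | both, at least 3 days |
| Restart limit | 3 weeks | 4 weeks |
| Condition | marrow toxicity recovered | marrow toxicity recovered |
| Start of window | not stated | not stated |
| Reference to the other section on restart timing | none | none |

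**Step 1: is it the same event?** The term in 6.8.5 is the broader one and includes the term in 7.7. Section 7.7 bars radiotherapy during treatment except palliative treatment of bony metastases present at baseline. For any patient treated as the protocol allows, both restart sentences therefore apply.

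**Step 2: how wide is the conflict?** Take a common start date for both windows.

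- Limit in 6.8.5: 3 × 7 = 21 days.
- Limit in 7.7: 4 × 7 = 28 days.
- Difference: 28 − 21 = 7 days. A restart on days 22 to 28 meets 7.7 and not 6.8.5. A restart by day 21 meets both; a restart after day 28 meets neither.

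**Step 3: could different start dates explain the difference?** Suppose the 7.7 window runs from the day the drugs are stopped and the 6.8.5 window starts s days later. Counted from the stop, the limits are 28 and 21 + s, so the gap is 28 − (21 + s) = 7 − s days.

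- With s = 3, the minimum stop before radiation, the gap is 4 days.
- The limits coincide only if s = 7.

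The 3-day stop appears in both sections and does not by itself account for the difference. Because no start date is given in either place, s is unknown and sites cannot settle the conflict by counting.

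**Step 4: does it reach the analyses?**

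- Objective response (SAP 3.2.1): radiotherapy does not count as subsequent anti-cancer therapy for this endpoint, and restart timing does not enter the definition. There is no effect.
- Time to discontinuation or death (Protocol 8.4.2, SAP 3.2.2): the endpoint runs to discontinuation or death. An interruption that ends in restart does not change it.
- Actual exposure (SAP 3.3.1): total interruption time is subtracted as it occurred. The calculation works under either limit; a restart at day 28 and one at day 21 differ by at most 7 days for that patient.
- Important deviations (SAP 2.2): restart timing is not among the listed categories. It could enter only through the review of monitoring notes, where the reader would meet two standards.

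**The case against.** The strongest reply is that little turns on this. Both sentences are advisory in wording and depend on marrow recovery. Permitted radiotherapy is confined to a narrow indication, and only patients who restart in the disputed week are affected. All of that stands, and it keeps the point minor. It does not remove the conflict, because both sentences are operative text and neither yields to the other.

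One could also argue that 6.8.5 speaks of radiation in general and 7.7 of palliative radiation, so that the specific rule displaces the general one. The protocol does not say so, and since 7.7 allows no other on-treatment radiotherapy, that reading would leave the 6.8.5 sentence with no permitted case to govern.

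Three stronger readings are tempting, and the documents do not support them.

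- **That the 4-week figure also breaks a general cap in Section 6.8.** That section does say: "The time a given drug is held should not exceed 3 weeks". The sentence sits in the text on managing drug-related toxicity, directly after a provision for holding the drug to which a toxicity is attributed. A planned stop of both drugs for radiotherapy falls under 6.8.5, so the sentence is not evidence here.
- **That a late restart leads to discontinuation, and so shifts time to discontinuation.** Under 6.8.5, going past 3 weeks for an intercurrent condition calls for a discussion with the study physician. Section 3.9 does not list a late restart after radiotherapy as a reason to discontinue.
- **That every patient given palliative radiotherapy is affected.** Only a restart between the two limits is.

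**Conclusion.** The inconsistency is real and the text is wrong as written, but it is minor. Sections 6.8.5 and 7.7 set limits that differ by 7 days for the only on-treatment radiotherapy the protocol permits, and the missing start date compounds the ambiguity. The days 22 to 28 result assumes that both windows begin on the same date, which neither section states.

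The documents give no frequency of bone metastases or of palliative radiotherapy, so the number affected among the approximately 60 planned patients cannot be estimated and may be zero. The consequence is confined to how sites handle, escalate and record such patients. The primary response-rate analysis is unaffected, and there is no documented effect on time to discontinuation or death. This review takes no position on which interval is right.

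**What to change.** Reconcile Protocol 6.8.5 and 7.7 to one restart window, ideally stated once and cross-referenced from the other section. State the date it is counted from, for example the stop of study drugs, the first radiation fraction or the last. Changing only the number would leave that ambiguity in place. Make the result consistent with the sentence in 6.8.5 on discussion with the study physician, so that a site can tell whether and when that discussion applies after radiotherapy. The clinical team must decide the interval and the start point.

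The cost is a wording change in two paragraphs and a letter to sites. No statistical analysis needs to change.

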7. INVESTIGATIONAL PRODUCT AND OTHER TREATMENTS

7.1 Identity of investigational product(s)

Table 17 Identity of investigational product(s)

Investigational product ^a	Dosage form and strength	Manufacturer
Olaparib	150 mg and 100 mg tablet	Abbvie on behalf of AstraZeneca
Cediranib	20 mg and 15 mg tablet	AstraZeneca

a Descriptive information for olaparib and cediranib can be found in the respective olaparib and cediranib Investigator's Brochures

7.1.1 Cediranib

Cediranib is available as a beige film-coated tablet containing 20 mg or 15 mg of cediranib. Patients will be administered cediranib study treatment tablets orally at a dose of 30 mg od. The planned dose of 30 mg od will be made up of 2 × 15 mg tablets od. One x 20 mg and 1 x 15 mg tablets will be used to manage dose reductions.

The dose of cediranib can be taken at the same time as the morning dose of olaparib and can be taken with or without food, in a similar way each morning.

7.1.2 Olaparib

Olaparib is available as a green film-coated tablet containing 150 mg or 100 mg of olaparib. Patients will be administered olaparib study treatment tablets orally at a dose of 200 mg bd. The planned dose of 200 mg bd will be made up of 2 × 100 mg tablets bd. One x 150 mg and 1 x 100 mg tablets will be used to manage dose reductions.

The olaparib tablets should be swallowed whole and not chewed, crushed, dissolved or divided. Olaparib tablets can be taken with or without food.

